1.0 Research Design

1.1 Purpose/Specific Aims

The purpose of the study is to investigate how exposure to Perfluorononanoic acid (PFNA) modifies immune responses to vaccination. We hypothesize that PFNA suppresses the innate immune response to vaccine stimulus, consequently leading to a decrease in antibody production. To assess relationships between exposure to PFAS and innate and acquired immune responses to a vaccine stimulus, we will use a combined approach involving omics technologies and traditional immunological assays. This study is a supplement to an existing protocol ("Human health effects of drinking water exposures to per- and poly-fluoroalkyl substances (PFAS): A multi-site cross-sectional study", Pro2020001052).

A. Objectives

1. Evaluate associations between PFAS levels, markers of innate immune activation, and changes in specific antibody levels.
2. Investigate the relationship between PFNA levels and modifications in immune specific transcriptomic and metabolomic responses to vaccination.

B. Hypotheses / Research Question(s)

We hypothesize that increasing PFNA exposure is associated with a suppressed innate immune, measured as pro-inflammatory cytokines and CRP, which leads to a diminished antibody response to vaccination. We aim to use transcriptomic and metabolomic pathway analysis to identify cellular responses that support this hypothesis.

1.2 Research Significance

Exposure to per- and polyfluoroalkyl substances (PFAS), recognized as "forever" chemicals due to their persistent nature, poses a significant threat to public health. With more than 98% of Americans having detectable levels of PFAS in their blood, these compounds have been linked to immune suppression by observations of increased infectious disease risks and diminished antibody response to vaccination, including routine tetanus-diphtheria vaccination in children [1-15]. Previous studies have demonstrated differences in the time course of production of specific IgG following tetanus-diphtheria (Td) vaccination in a small study of 12 adult participants over 7 time points in a 30-day period [6]. The proposed study will focus on exposure to Perfluorononanoic acid (PFNA) in Paulsboro, NJ, and add measurement of innate immune responses following the vaccine stimulus. The results of this study will increase knowledge about immunotoxicity resulting from PFAS exposure, which has been determined to be the critical effect for human health risk assessment by the U.S. EPA (Environmental Protection Agency) and EFSA (the European Food Safety Authority) [16,17]. The most recent scientific reviews of immunotoxic PFAS endpoints highlight the need for more relevant longitudinal human studies, and probing the immune response through vaccination has been a standard approach [18-20]. We will measure several markers of immune response in serum and oral fluid samples using standard immunoassays and targeted metabolomic analysis. An innovative aspect of our approach is the pilot testing of oral fluid collection as a less burdensome method, compared to venipuncture, for serial measurement of immune responses in epidemiological studies. Oral fluid (OF) is a biofluid that is a mixture of saliva and non-salivary components, which contains both innate and adaptive immune components, including specific immunoglobulins and cytokines [21-30]. OF has been shown to be a reliable biomatrix for detecting antibodies that represent serum concentrations, even though antibodies in this fluid are often found in lower concentrations when compared to serum. If found to be feasible and reliable in this study, this method will be useful in future community-based studies of immune response where repeated blood draws can often be a major barrier. Overall, this research project is crucial step in developing rational and effective measures to protect public health in the face of widespread PFAS exposure.

1.3 Research Design and Methods

HRP-503a-TEMPLATE-Interventional Research Protocol 1.11.22

Protocol Title: PFAS Exposure and Immune Response

Protocol Version: 3

Protocol Version Date: July 11, 2024

PI: [name], MPH, CIH, DABT

This study is a pre-post clinical trial. We will assess the impact of PFAS immune responses to routine booster vaccination against Tetanus-Diphtheria (Td) over a 30-day period among 20 adults recruited from a community in New Jersey that had drinking water contaminated with PFAS, predominantly PFNA. Within the larger study, 775 adults had serum PFAS measurements between July 2021 and September 2023. ("Human health effects of drinking water exposures to per- and poly-fluoroalkyl substances (PFAS): A multi-site cross-sectional study", Pro2020001052). For this study, we will recruit participants from the participants in the larger study who agreed to be contacted for future studies.

A. Research Procedures

All study visits will take place in the local Rutgers study office space ([name]) used for the main study. At study visit 1, participants will then have their blood drawn (15 mL) by venipuncture by trained research staff. Total amount of blood collected at visit one will be 15 mL (1 tablespoon). Participants will self-administer their oral fluid collection using the Oracol sampler (<https://www.malmed-oracol.co.uk/products/oracol/>) by swabbing their gumline for 1-2 minutes under the supervision of research staff. After baseline sample collection, participants will be given a Td booster vaccination. The second, third, and fourth study visits will occur 24, 48, and 72 hours after the first visit to capture the innate immune response, while visits five, six, and seven will take place 7, 14, and 30 days after the first visit to capture the adaptive immune response. At study visits 2-7, participants will have venous blood drawn (15 mL each visit) and will collect their oral fluid using the Oracol sampler by swabbing their gumline for 1-2 minutes under the supervision of research staff.

Additionally, data collected about the subject collected in the main study (including serum PFAS levels, residential history, and history of Td vaccination) will be used in this study.

B. Data Points

Td specific antibody levels, cytokine levels, CRP, RNA transcripts and metabolites related to immune response and activation.

C. Study Duration

The study will take approximately one year. Individual participation will consist of 7 study visits over a 30-day period. The initial study visit should take less than 45 mins including the consent process and post-immunization observation period, while study visits 2-7 should take 15 minutes. Length of participation for each subject will be 30 days.

D. Endpoints-NA

1.4 Preliminary Data – NA

1.5 Sample Size Justification

Twenty subjects will be enrolled. Identifying exposures predicting immune and disease outcomes requires sufficient power to account for false positives due to multiple comparisons. The goal of 20 adult subjects for the vaccination study was selected after statistical power calculations using data from the modeled Kielson (2016) study were done. Assuming the Kielson et al. correlation of 0.761 between PFAS level and change in diphtheria antibody concentration, then 20 subjects we would have 98.5% power to detect that the correlation is different from zero. Thus, we should have adequate power to detect effect sizes similar to those reported by Kielson even with some attrition and participant drop out. We may see a larger correlation as we expect a larger spread in our distribution of PFAS, yielding greater power. However, even with a smaller correlation of 0.7, we would have 95% power.

1.6 Study Variables

HRP-503a-TEMPLATE-Interventional Research Protocol 1.11.22

Protocol Title: PFAS Exposure and Immune Response

Protocol Version: 3

Protocol Version Date: July 11, 2024

PI: [name], MPH, CIH, DABT

A. Independent Variables, Interventions, or Predictor Variables

Intervention: Participants will be immunized with TENIVAC, which is FDA approved booster vaccine against Tetanus and Diphtheria. Td antibody levels will be measured to determine post-vaccination antibody status.

B. Dependent Variables or Outcome Measures

Tetanus Toxoid IgG, Diphtheria Toxoid IgG, Cytokines, and CRP concentrations in serum and oral fluid. RNA sequencing, and LC/GC-HRMS to identify transcripts and metabolites of immune response in serum.

1.7 Drugs/Devices/Biologics

A. Schedule and Administration

Each subject will receive a Td vaccination at the first study visit following consent and distribution of vaccine information sheet (VIS). TENIVAC (Tetanus and Diphtheria Toxoids Adsorbed) is an active immunization for the prevention of tetanus and diphtheria in persons 7 years of age and older. TENIVAC will be administered intramuscularly as recommended in the subject's deltoid muscle at a dose of 0.5 mL which contains 5 Lf of Tetanus Toxoid and 5 Lf of Diphtheria Toxoid. Other ingredients per 0.5 mL dose include 1.5 mg of aluminum phosphate (0.33 mg of aluminum) as the adjuvant and ≤5.0 mcg of residual formaldehyde. Vaccinations will be administered only by medically qualified personnel.

B. Drug/Device Accountability and Storage Methods

TENIVAC, purchased as either single dose vials or prepared syringes will be stored at the local study site in a refrigerator between 2° to 8°C (35° to 46°F) per manufacture recommendation and secured behind a locked door only accessible to study staff. Detailed logs for vaccine storage, administration, and refrigerator temperature will be kept. Just before use, the single-dose vial or syringe will be shaken well until a uniform, white, cloudy suspension results. Preparation, and disposal of TENIVAC will be done by trained study staff/research assistants. Syringes and/or vials will be disposed of in the proper biohazard sharps container.

1.8 Specimen Collection

A. Primary Specimen Collection

- **Types of Specimens:** Blood and oral fluid samples. At each visit, blood samples (15 mL) will be collected using standard venipuncture performed by a phlebotomist. Oracol swabs will be used to harvest oral fluid rich with GCF (and will be self-collected by the participant under the direction and supervision of research staff by gently swabbing their gumline for 2 minutes. In total there will be 280 specimens collected for this study (7 blood samples + 7 saliva samples per subject x 20 subjects). All specimen collections will happen at the local study site, [name].
- **Annotation:** The blood and oral fluid samples will be labeled by a study ID and visit number. The same study ID will be used for samples/data collected in the main study as in the supplemental study.
- **Transport:** The blood and oral fluid samples will be collected at the Paulsboro Study site which is also approved by REHS for blood and saliva processing.
- **Processing:** The research assistants will process and aliquot the blood and oral fluid.
- **Storage:** The specimens will be stored in the -80°C freezer at the lab then transported to Rutgers EOHSI or shipped to the fee for service analytical lab (Comprehensive Laboratory for Untargeted Exposome Science (CLUES), Gangarosa Department of Environmental Health at Emory University) by a research assistant with IATA training.
- **Disposition:** Any excess specimens will be retained by [name] in a -80°C freezer at EOHSI (Room 232). Access to the freezer room is card controlled.

B. Secondary Specimen Collection - NA

1.9 Data Collection

A. Primary Data Collection

- **Location:** Subjects will be screened at the local study site in Paulsboro, either in person or over the phone.
- **Process of Data Collection:** Research assistants will do the screening.
- **Timing and Frequency:** Data collection will take place at screening, and at each visit.
- **Procedures for Audio/Visual Recording:** - NA
- **Study Instruments:** A screening questionnaire developed for this study will be used.
- **Ethnographic Studies, Interviews, Or Observation:** - NA
- **Subject Identifiers:** Subject's contact information (name, email, mailing address, and phone number) will be collected to schedule appointments. All documents will be coded by study ID and visit number entered directly into the REDCap database.

B. Secondary Data Collection-NA

2.2 Research Staff Training

Only staff working on the main study will also work on this supplement. The staff have been trained by [name] in study procedures.

3.0 Multi-Center Research - NA

4.0 Subject Considerations

4.1 Subject Selection and Enrollment Considerations

A. Method to Identify Potential Subjects

Adults who enrolled in the main study who consented to be contacted for future studies will be asked to participate in this study. We will recruit participants from the first and fifth quintiles of PFNA serum concentrations to maximize contrast in exposure, balanced recruitment from the first and fifth quintiles of exposure will be randomized.

B. Recruitment Details

The study will recruit only main study participants. Previous subjects, who completed their main study visit and consented to be contacted for future studies, will be called by a research assistant, and asked if they are interested in participating in a supplemental study. If so, an appointment will be made for a study visit.

C. Subject Screening

Subjects are screened for the main study. Adults who participate in the main study will be eligible for this supplemental study.

- **Inclusion Criteria**
Adults (18 years of age and older), weigh at least 110 pounds, and who participated in the main study may be eligible to participate in this supplemental study.
- **Exclusion Criteria**
 - Pregnancy
 - History of difficult blood draws
 - History of adverse reaction to prior vaccinations
 - Currently taking immune suppressants
 - Recent dental surgery or dental procedure within 4 weeks of starting study
 - Had a Td booster in the past 10 years

D. Privacy Protections

Prospective subjects are identified by their participation in the main study. Identifiers for the main study are stored in the study REDCap database. Only the study team has access to the database.

4.2 Obtaining Identifiable Information About Non-Subjects - NA

4.3 Number of Subjects

A. Total Number of Subjects

20 subjects will be enrolled.

B. Total Number of Subjects If Multicenter Study - NA

C. Feasibility

The main study recruited 775 adults and for the small number of subjects in this study, we expect to be able to complete recruiting and testing in a timely manner.

4.4 Consent Procedures

A. Consent Process

▪ Location of Consent Process

Consent will take place in the local study office in Paulsboro.

▪ Ongoing Consent

Study activities will be discussed with the subject at the start of each visit. All questions will be answered.

▪ Individual Roles for Researchers Involved in Consent

Screening and consenting may be done by the coordinator or a research assistant.

▪ Consent Discussion Duration

We expect the consent process to take approximately 10 minutes. The study visit will take place immediately after the consent.

▪ Coercion or Undue Influence

Only main study adult volunteers will be asked to participate in the supplemental study. The consent form will clarify that participation in the supplemental study is not required.

Subject Understanding

The key study elements will be specifically mentioned during the consent discussion and all questions will be answered.

▪ Protecting Privacy

Consent discussions will take place in a private office prior to participation. No additional information about the subject will be collected until after consent is obtained.

B. Waiver or Alteration of Consent Process - NA

HRP-503a-TEMPLATE-Interventional Research Protocol 1.11.22

Protocol Title: PFAS Exposure and Immune Response

Protocol Version: 3

Protocol Version Date: July 11, 2024

PI: [name], MPH, CIH, DABT

C. Documentation of Consent

▪ **Documenting Consent**

The consent form will be stored in REDCap. Both the participant and study investigator will sign the consent form. A copy of the signed consent form will be emailed to the participant.

▪ **Waiver of Documentation of Consent (i.e., will not obtain subject's signature) - NA**

4.5 Special Consent Populations - NA

A. Enrolling Minors-Subjects Who Are Not Yet Adults - NA

B. Enrolling Wards of the State - NA

C. Enrolling Non-English-Speaking Subjects - NA

D. Enrolling Adults Lacking Decision-Making Capacity (Surrogate Consent) - NA

E. Special Consent Considerations - NA

4.6 Economic Burden and/or Compensation for Subjects

A. Expenses - NA

The subject is not expected to incur any expenses.

B. Compensation/Incentives

Subjects will be paid \$50 for each study visit (up to \$350 total).

C Compensation Documentation

Compensation will be documented in REDCap. Subjects will also be asked to sign the subject voucher for cash payments.

4.7 Risks of Harm/Potential for Benefits to Subjects

A. Description of Risks of Harm to Subjects

▪ **Reasonably Foreseeable Risks of Harm**

Td Vaccination: Pain, redness, or swelling where the shot was given, mild fever, headache, feeling tired, and nausea, vomiting, diarrhea, or stomachache sometimes happen after Td vaccination. People sometimes faint after medical procedures, including vaccination. As with any medicine, there is a very remote chance of a vaccine causing a severe allergic reaction, other serious injury, or death.

Venipuncture: Slight pain, some bleeding, or bruising may occur when blood is drawn. A total of 105 ml of blood (15 ml per study visit over a 30-day period) will be required for the planned assays.

Oral fluid collection: When swabbing the gumline, there may be minor bleeding if done too roughly.

▪ **Risk of Harm from an Intervention on a Subject with an Existing Condition**

The study will not enroll subjects with existing conditions related to adverse vaccination responses.

▪ **Other Foreseeable Risks of Harm**

There is a risk of possible loss of confidentiality, but no sensitive information is collected in the study.

- **Observation and Sensitive Information – NA**

- B. Procedures which Risk Harm to Embryo, Fetus, and/or Pregnant Subjects -NA**

- C. Risks of Harm to Non-Subjects -NA**

- D. Assessment of Social Behavior Considerations - NA**

- E. Minimizing Risks of Harm**

All subjects will be screened prior to scheduling. Subjects with a history of adverse reactions to vaccination and difficulty with blood draws are excluded from the study out of an abundance of caution. All female subjects will receive a urine pregnancy test prior to vaccination. Subjects will be informed in the consent document that they will be given the results of the pregnancy test. Although Tetanus-Diphtheria is a routine vaccination, subjects will be provided with a vaccine information sheet (VIS) before vaccination to review all information, including risks associated with the specific vaccine type. The physician PI will be onsite to administer the vaccine and respond to any immediate reactions. Following vaccination, subjects will be visually monitored by medical personnel for at least 15 minutes. In case of anaphylactic or acute hypersensitivity reactions, Epinephrine hydrochloride solution (1:1,000) or other appropriate agents and equipment will be available for immediate use, and 911 will be called. In the case of any adverse event, the event will be documented, and a report will be sent to Vaccine Adverse Event Reporting System (VAERS) and IRB.

- **Certificate of Confidentiality - NA**

- **Provisions to Protect the Privacy Interests of Subjects**

All data and specimen will be coded by a Study ID. All identifiable information will be stored in REDCap and accessible only to the study team.

- F. Potential Direct Benefits to Subjects**

Subjects will be boosted against Tetanus and Diphtheria.

5.0 Special Considerations

5.1 Health Insurance Portability and Accountability Act (HIPAA) - NA

5.2 Family Educational Rights and Privacy Act (FERPA) - NA

5.3 Code of Federal Regulations Title 45 Part 46 (Vulnerable Populations) - NA

5.4 General Data Protection Regulation (GDPR) - NA

5.5 NJ Access to Medical Research Act (Surrogate Consent) - NA

6.0 Data Management Plan

6.1 Data Analysis

Means, standard deviations, percentiles and histograms will summarize the distributions of outcome variables. Based on Kielsen (2016), we expect exponential rise in plasma antibody concentrations from 4 to 10 days. Thus, in the primary analysis, we will examine the linear increase in log of antibody concentrations from 4 to 10 days and whether that increase is modified by exposure to pfas through an interaction term between time and PFAS (log-transformed). Integration of exposure, metabolic response, and immune response has the potential to provide key insight into mechanisms underlying

exposure mediated immune suppression following Td vaccine. To examine the assumption that there's a linear increase from 4 to 10 days, linear models with cubic splines relative to time since immunization will assess goodness of fit across different strata of PFAS exposures. If the time of increase varies substantially from the 4 to 10-day assumption, then the initial linear models will be adjusted accordingly.

To investigate associations between RNA-seq and metabolomics data with PFAS exposure levels, differential analysis will identify genes and metabolites with altered expression/abundance across exposure groups. Pathway analysis will assess biological relevance by examining enrichment of gene sets and metabolic pathways. Correlation analysis will evaluate the relationship between individual gene expression/metabolite levels and PFAS exposure. Longitudinal analysis will assess temporal changes in both RNA-seq and metabolomics data following vaccination. Analyses will be adjusted for confounders, corrected for multiple testing, and assume stable PFAS concentrations over time. This comprehensive approach will elucidate the dynamic relationship between molecular profiles and PFAS exposure, advancing our understanding of PFAS toxicity and its impact on human health. For analyzing the oral fluid samples, as a feasibility/proof of concept study, no power calculations have been done. Accuracy will be assessed by comparison to ELISA reference methods by paired t-test and correlation analysis to examine overall bias and reliability. The Bland Altman plot will assess bias and homogeneity of error relative to ELISA across the range of values. Mean, standard deviations, and coefficients of variation will be calculated to benchmark the method for reference in future studies.

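### The primary day 4–10 antibody slope has only one scheduled draw (day 7) inside its window, and section 6.1 fixes no visit set, antigen or adjustment rule that would define what is estimated instead

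*Combined protocol and SAP*

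**What the plan says.** Section 6.1 (Data Analysis) expects antibody to rise exponentially between days 4 and 10. For the primary analysis it says "we will examine the linear increase in log of antibody concentrations from 4 to 10 days", and it tests whether log-transformed PFAS modifies that increase through an interaction with time.

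The sampling schedule is in section 1.3 A. After the baseline draw, "The second, third, and fourth study visits will occur 24, 48, and 72 hours after the first visit"; then "visits five, six, and seven will take place 7, 14, and 30 days after the first visit to capture the adaptive immune response". Section 1.8 A confirms seven blood samples per participant.

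To check the window, section 6.1 says "linear models with cubic splines relative to time since immunization will assess goodness of fit across different strata of PFAS exposures". It continues: "If the time of increase varies substantially from the 4 to 10-day assumption, then the initial linear models will be adjusted accordingly". It gives no knots, visit set, visit windows or criterion.

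Section 1.6 B lists the outcomes as "Tetanus Toxoid IgG, Diphtheria Toxoid IgG, Cytokines, and CRP concentrations in serum and oral fluid"; section 6.1 does not say which antibody is primary. The hypothesis in section 1.1 concerns PFNA ("We hypothesize that PFNA suppresses the innate immune response to vaccine stimulus, consequently leading to a decrease in antibody production"), and section 4.1 A samples participants by PFNA quintile, but section 6.1 says only PFAS. Section 1.3 D marks endpoints as not applicable, so nothing there settles these choices.

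**The concern.** A slope over days 4 to 10 needs at least two time points in that interval, and the schedule gives one. The analyst must therefore bring in visits from outside the window, and the plan does not say which. Two analysts following section 6.1 faithfully could fit different models and report different primary results.

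This matters most if exposure affects when antibody rises as well as how fast. Section 1.2 makes that a relevant possibility, since it cites "differences in the time course of production of specific IgG following tetanus-diphtheria (Td) vaccination in a small study of 12 adult participants". It gives no size for any delay.

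The safeguard has the same weakness. The spline check relies on the same seven visits, is examined by PFAS stratum, and can lead to a changed primary model with no stated rule.

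**Working it through.** **1. The plan's own power figures.** Inputs from section 1.5: n = 20, r = 0.761 and r = 0.7. Alpha is not stated; two-sided 0.05 is assumed. Fisher z power = Φ(atanh(r)·√(n−3) − 1.960).
- r = 0.761: Φ(0.9986 × 4.123 − 1.960) = Φ(2.157) = 98.45% (stated 98.5%).
- r = 0.7: Φ(0.8673 × 4.123 − 1.960) = Φ(1.616) = 94.7% (stated 95%).

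Both reproduce. They concern one antibody change per participant, not a time by PFAS interaction.

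**2. Estimability inside the window.** Of days 0, 1, 2, 3, 7, 14 and 30, only day 7 lies in days 4–10. The model's columns are 1, t, P and t·P, where P is log PFAS. With t = 7 throughout, t is 7 times the intercept and t·P is 7 times P, so the rank is 2 of 4. Neither the slope nor the interaction is estimable. With days 3 and 7, 3 and 14, 7 and 14, or 3, 7 and 14, the rank is 4 of 4.

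**3. Can the schedule verify the window?** Assume log antibody is flat, then rises linearly, then is flat.
- Rise on days 3–11 at rate 0.75: day 7 = 4 × 0.75 = 3; final = 8 × 0.75 = 6.
- Rise on days 4–10 at rate 1.0: day 7 = 3; final = 6.
- Rise on days 5–9 at rate 1.5: day 7 = 2 × 1.5 = 3; final = 4 × 1.5 = 6.

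All three give 0, 0, 0, 0, 3, 6, 6 at the seven visits. A two-fold range of true rates is indistinguishable, and no spline can separate them. When the day 4–10 curve is true, cubic splines over all seven visits return 0.51 to 1.93 times the true slope across eight knot choices tried.

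**4. What each visit set estimates.** Least-squares slope b = Σ(t − t̄)y / Σ(t − t̄)², with true rate 1. The delayed column has the same rate and total rise, one day later (days 5–11); the one-day delay is an assumption.

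| Visits used | Rise days 4–10 | Rise days 5–11 | Apparent effect of delay |
|---|---|---|---|
| 3, 7 | 3/4 = 0.750 | 2/4 = 0.500 | −33% |
| 3, 14 | 6/11 = 0.545 | 6/11 = 0.545 | 0% |
| 3, 7, 14 | 33/62 = 0.532 | 34/62 = 0.548 | +3% |
| 7, 14 | 3/7 = 0.429 | 4/7 = 0.571 | +33% |
| 7, 14, 30 | 30/278 = 0.108 | 40/278 = 0.144 | +33% |
| all seven | 0.234 | 0.236 | +0.7% |

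For a delay of d days (d up to 3), the effect is −d/3 on days 3 and 7, +d/33 on days 3, 7 and 14, and +d/3 on days 7 and 14 or 7, 14 and 30. For d from 0.5 to 2 these run −17% to −67%, +1.5% to +6%, and +17% to +67%.

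**5. Common timing.** If PFAS lowers the rate by 25% without shifting its timing, every value of y is multiplied by 0.75 and every set gives −25%. The visit choice then only rescales the slope.

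**6. The replacement contrasts.** The day 0 to 14 change equals 6 for any delay up to 4 days (0% effect); at 5 days it is 5 (−17%). The day 0 to 7 change is 3 − d, or −33% for one day.

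**The case against.** The strongest reply is that section 6.1 does not tell the analyst to discard visits outside days 4–10. Any competent analyst would use neighbouring ones, and the model then has full rank. That stands: a reader might infer that the primary analysis cannot be run at all, and the documents do not support so much. What remains is that no visit set is chosen, and that no choice from this schedule recovers the day 4–10 rate without assumed break days.

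A reader might also infer that the open adjustment inflates the type I error by a known amount. It cannot be quantified: the adjustment depends on the time of increase, not on p-values, and any figure would reflect which alternative visit sets one chose to list. The supportable point is qualitative: the primary can change after the data have been seen by PFAS stratum, with no criterion.

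Nor is the exposure truly in doubt. Sections 1.1, 1.2 and 4.1 A point to PFNA; section 6.1 only needs to say so.

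Finally, a day 0 to 14 change answers a question about size of response, whereas section 6.1 asks about rate. That is a real cost. Prespecifying a slope's visits would stay closer to the sponsor's question, so that option is kept below. Measuring the rate within the window would need a further draw there.

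**Conclusion.** The point holds and should be fixed before outcome data are examined. One of seven scheduled draws lies in the primary window. The stated slope and interaction are not estimable from in-window data, and the planned check cannot confirm the window.

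The consequence depends on timing. With timing common to all PFAS levels, the visit choice rescales the slope and does not distort the relative PFAS effect. With an assumed one-day delay at higher PFAS, the apparent effect ranges from −33% to +33% across reasonable visit sets; +33% also arises on days 7, 14 and 30, the visits section 1.3 A assigns to the adaptive response. These figures rest on nominal visit days, a flat–linear–flat curve and an assumed delay.

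A reader might infer that the sample size calculation is wrong. It is not: both figures reproduce. The gap is that the documents do not tie the correlation of 0.761 to a PFAS compound, visits or a log scale.

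**What to change.** In section 6.1, before outcome data are examined:
- **Primary:** replace the day 4–10 slope with the change in log serum diphtheria IgG (the antigen used in section 1.5) from day 0 to day 14, one value per participant, regressed on log PFNA, with any covariates named. Day 14 is the first scheduled visit after the expected rise ends.
- **Secondary:** the day 0 to day 7 change, which is sensitive to timing, and tetanus IgG.
- **If a slope is kept as primary:** fix its visits in advance, for example days 3, 7 and 14, and describe it as the average rise over those visits, not the day 4–10 rate.
- **Any piecewise model over all seven visits:** secondary only, described as total rise under assumed break days, with a random participant slope on the rise.
- **Splines:** treat spline-chosen windows as sensitivity analyses, and delete for the primary the sentence "If the time of increase varies substantially from the 4 to 10-day assumption, then the initial linear models will be adjusted accordingly".

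In section 1.5, state that r = 0.761 is an assumption carried over to the new endpoint, exposure and scale.

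The cost is wording in two sections, with no new visits, samples or participants. The downsides are that the day 0 to 14 change measures size of response rather than rate, would not register a pure delay of up to 4 days, and loses participants without a day 14 sample. With 18 evaluable, the same power formula gives 97.2% at r = 0.761 and 91.9% at r = 0.7.
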